Effects of neural response on relapse vulnerability: Our primary outcome combines adherence to treatment and frequency of illicit opioid use during treatment. The primary outcome is a binary indicator of treatment success: if a patient provides ≥ 2 weekly UDS positive for opioids, or self-report of \geq two or more periods of ≥ 3 days of opioid use, or refuses XRNTX or XRBUP, or drops out of treatment entirely, then they will be classified as a treatment failure; otherwise they will be classified as a treatment success. We will calculate the PRE-ON change in %-signal-change for each of the regions and neural responses described in the R61 phase. We will use logistic regression models to predict the log-odds of treatment success (Aitkin et al 2009). The predictors in the model will be a binary factor for Group (XRNTX vs. XRBUP), and the neural change scores. We anticipate that there will be some greater PRE to ON changes in the XRNTX group than in the XRBUP group, so there will be some confounding between the effects of change score and the effects of Group on the rates of positive UDS. Thus, we will include Group first in our model, so evaluating the Group effect separate from the change-score effects, and then include the change scores in a model including Group, so evaluating the additional effect of change-scores in addition to the existing effects of Group. To assess whether the effects of the change scores differ between the XRNTX and XRBUP groups, we will also test for interaction effects between Group and each of the change-scores, by adding the interaction terms to the model that includes the group and neural change score main effects. We will check the assumptions underlying the logistic regression models (e.g. linearity of covariates effects on log-odds, outliers, influential observations) using standardized residuals, influence diagnostics, and graphical displays.

Sample size considerations for the sample: Analyses of Session by Group effects on neural response: For a one-sided test that the PRE vs ON effect is larger in the XRNTX group than in the XRBUP group, our sample of 70 per group yields 81% power for an effect of $d=0.42$ or greater. This effect is similar to the effects observed in the preliminary data. On the basis of the preliminary data we anticipate Group by Session effects of approximately $d=0.38$ in the VS and $d=0.42$ in the mOFC.

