Analyses of effects of neural response on relapse vulnerability: We consider the effect for an individual neural change variable, in a model where Group is included, assuming a small effect for Group (odds ratio = 1.25). We have three domains, with two neural variables in two domains and one in the other, so we provide power for $\alpha=0.05$ and for $\alpha=0.025$. For $\alpha=0.05$ we have 80% power for an odds ratio of 1.75 or higher per standard deviation increase in a neural variable; for $\alpha=0.025$, we have 80% for an odds ratio of 1.86 or higher.

Analyses of polysubstance use outcomes: We will also examine the effects of Group and neural change variables on other substance use outcomes, including self-report and UDS measures of opioid, stimulant, and benzodiazepine use. Here, we will use the self-report and UDS measures to create binary weekly measures of use for each substance, and use GEE repeated measures logistic regression models, with Group and the neural change measures as predictors, to estimate and test effects. These secondary analyses will be subject to missing data. We anticipate 25% dropout rates. To assess possible effects of nonignorable missingness on inference, we will perform sensitivity analyses using pattern-mixture models and selection models. For pattern mixture models, subjects are grouped on the basis of their pattern of missing data, and the resulting categorical factor is included in the analyses as a main effect and interaction with predictors of interest. Overall predictor effects may be found by averaging over the patterns (Molenberghs et al 2005). Selection models (Molenberghs et al 2005) take a different approach, by explicitly modeling the probability of drop out, and incorporating the predicted probabilities into the main longitudinal analysis, with the dropout and response processes included in a single bivariate model. Comparisons between the predictions of the primary analyses, and each set of pattern mixture and selection models, provides some evidence for assessing the sensitivity of results to missing data.

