13 APPENDIX

13.1 Schedule of Activities (SoA)

	Screening detox and randomization (Day -14)	MRI Scan 1 Baseline (day 0)	Induction to XRBUP or XRNTX (day 0-10)	Injection 1 (day 10) + weekly follow up	Injection 2 (day 40)	MRI Scan 2 On Treatment (day 55)	Injection 3 (Day 70)	Weekly Follow- up End of study and referral (Day 100)
Psychiatric and medical								
Demographics (age ¹ , sex ¹ , edu ¹)		X						
History, physical and labs (C.4.a)		X						
SILS		X						
MINI (EOS* – end of study)		X						X EOS*
Addiction Severity Index ¹		X						X EOS*
Clinical/Behavioral (C.3.a)								
HAM-D ² , HAM-A ² , COWS ²	X	X	X		X	X		X
SOWS, Opioid Craving Scale ² , SF-MPQ-2 ² , STAI-6		X	X	X	X	X		X
TLFB interview	X	X	X		X	X		X
Ten-drug urine drug screen (UDS)	X	X	X	X	X	X		X
Go-NoGo errors of commission ²		X		X				
Neuroimaging (Section C.3.b)								
Go-NoGo fMRI ³		X			X			
Opioid Cue task fMRI ³		X			X			
Resting-state fMRI ³		X			X			
MPRAGE (anatomical MRI scan)		X			X			

PRINCIPAL INVESTIGATOR SIGNATURE

STUDY SPONSOR: [name]

STUDY TITLE: **Open label comparison of injectable extended release preparations of buprenorphine (Brixadi®) and naltrexone (Vivitrol®) for the treatment of opioid use disorder**

STUDY ID 843403

PROTOCOL VERSION V5.0

I have read the referenced protocol. I agree to conduct the study in accordance to this protocol, in compliance with the Declaration of Helsinki, Good Clinical Practices (GCP), and all applicable regulatory requirements and guidelines.

Principal Investigator Name	[name]	Signature
Affiliation:	University of Pennsylvania	Date 7/17/2023

END OF DOCUMENT

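### The weekly substance-use models put Group and the on-treatment neural change scores in together, so their Group coefficient is a residual given brain change and not the drugs' effect on use

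*Combined protocol and SAP*

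**What the plan says.** In section 9.1, the paragraph on polysubstance outcomes states its aim: "We will also examine the effects of Group and neural change variables on other substance use outcomes". The outcomes are binary weekly indicators of opioid, stimulant and benzodiazepine use, built from self-report and urine screens. The model is to "use GEE repeated measures logistic regression models, with Group and the neural change measures as predictors, to estimate and test effects". No order of entry and no Group-only model is given, and the paragraph calls these analyses secondary.

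The neural predictors are defined just before, under relapse vulnerability: "We will calculate the PRE-ON change in %-signal-change for each of the regions and neural responses described in the R61 phase". The schedule of activities puts the ON scan at day 55, while weekly follow-up starts with the first injection at day 10.

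For the binary treatment-success outcome, the same section expects the scores to differ by drug ("We anticipate that there will be some greater PRE to ON changes in the XRNTX group than in the XRBUP group") and draws the consequence: "there will be some confounding between the effects of change score and the effects of Group on the rates of positive UDS". Its remedy for that outcome is explicit: "Thus, we will include Group first in our model, so evaluating the Group effect separate from the change-score effects". The polysubstance paragraph neither repeats this step nor refers back to it. Section 9.4.1 mentions mixed models, selection models and a complier analysis, but specifies no Group-only model of weekly use.

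**The concern.** A predictor measured after randomisation, and itself expected to respond to treatment, changes what the Group coefficient means. With the change scores in the model, the Group test asks whether the drugs differ among people with equal brain change. The stated aim is whether the drugs differ in use.

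If the coefficient is read as the drug effect, it can mislead in two directions. Where the drugs differ in use because they differ in brain response, which is the trial's own theory, adjustment removes the effect. Where the drugs do not differ in use and the scores partly mark a patient trait linked to use, adjustment creates a Group difference.

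Section 3.2 lists opioid-positive urine screens as a primary clinical endpoint and section 3.3 lists cocaine-positive screens as secondary. The polysubstance paragraph gives the only stated model of weekly use of these substances by drug.

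**Working it through.** **1. The plan's drug-to-brain figure.** Section 9.1 gives 81% power for d = 0.42, one-sided, 70 per group. With alpha 0.05 (assumed, as it is not stated there): 0.42 × √(70/2) = 2.485; 2.485 − 1.645 = 0.840; Φ(0.840) = 0.80. This reproduces. No power is stated for the substance-use models.

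**2. How much of a Group effect could pass through the scores.** Inputs from section 9.1: anticipated d of 0.38 (VS) and 0.42 (mOFC); detectable odds ratios of 1.75 and 1.86 per SD of one neural variable; Group odds ratio 1.25. The odds ratios are stated for treatment success, and applying them to weekly use is an assumption.

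- Path through one score = d × ln(OR per SD) = 0.42 × ln 1.75 = 0.42 × 0.560 = 0.235, OR 1.27 (range 1.24 to 1.30 over the inputs).
- If the total Group OR were 1.25: ln 1.25 − 0.235 = 0.223 − 0.235 = −0.012, leaving OR 0.99 (range 0.96 to 1.01).
- If 1.25 is instead the OR given brain change: 0.223 + 0.235 = 0.458, a total OR of about 1.58.

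Adding log odds ratios is approximate in a logistic model, so this was simulated (500 trials, 70 per arm, 12 weekly outcomes, one score, d = 0.42, OR 1.75). With a fully mediated effect, the Group OR was 1.21 in the Group-only model and 1.00 in the joint model. With a conditional OR of 1.25, it was 1.46 against 1.23, and Group was rejected in 52% against 22% of trials.

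**3. False rejection when the drugs do not differ in use.** Let score j = trait j + shift j × Group, and let use depend on the traits only. Writing trait as score minus shift, the log-odds of use contain −Σ(βj × shift j) × Group. That is the Group coefficient in the joint model although the true Group effect is zero. It is on the participant-specific scale; GEE estimates lie nearer 1.

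Simulation assumptions: 70 per arm, 12 weeks, two-sided 5%, five scores correlated 0.3, random-intercept SD 1.5, intercept −0.8, robust standard errors, no dropout. The correlation, SD and intercept are not in the plan. The mOFC figure stands in for mPFC, the region named in H1a.

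| Shifts; OR per SD | −Σβ × shift | Implied OR | Joint test rejects |
|---|---|---|---|
| Cue regions only (0.38, 0.42); 1.25 on all five | −0.80 × 0.223 = −0.179 | 0.84 | about 8% |
| Cue regions only; 1.75 on all five | −0.80 × 0.560 = −0.448 | 0.64 | 29% |
| One active score (shift 0.42) at 1.75 | −0.42 × 0.560 = −0.235 | 0.79 | 11–13% |
| All five shift 0.42; 1.25 each | −2.10 × 0.223 = −0.469 | 0.63 | 31–32% |
| All five shift 0.42; 1.75 each | −2.10 × 0.560 = −1.175 | 0.31 | over 90% |

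The Group-only model stayed near nominal (4% to 7% across runs). Simulation error is about 2 points at the low rates: with 1,000 replicates, 2 × √(0.1 × 0.9/1000) = 0.019.

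**4. Lost effect under full mediation.** The joint model rejects at about 5% (5% to 7% across runs), whatever the total effect. Group-only power depends on that total: 15% with cue-only shifts at OR 1.75, and 69% to 75% with all five scores shifted at OR 1.75.

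**5. Who and when.** The joint model needs both scans, so participants without an ON scan leave it. Of the follow-up from day 10 to day 100, (55 − 10)/(100 − 10) = half precedes the scan that supplies the predictor.

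**The case against.** The strongest reply is textual. The treatment-success paragraph introduces its own model in similar shorthand, naming Group and the change scores as the predictors, and only then explains the order of entry. The polysubstance paragraph says it will also examine these effects, so the Group-first order may be meant to carry over. It may be, but nothing says so, and two analysts following the text could fit different models. The reply turns this into a request for explicit wording; it does not remove the need for one.

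A second reply is that the joint model suits the mechanistic question. That stands: it is the right model for testing the scores given Group. The problem is confined to reading its Group coefficient as the drug effect.

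The third reply concerns size, and it stands too. A reader might infer from the plan's figures that the Group test is almost always wrong. The documents do not support that. They anticipate d of 0.38 in VS and 0.42 in mOFC only, and the odds ratio of 1.75 is what can be detected for one neural variable on treatment success. The rejection rate above 90% needs a shift of 0.42 and an odds ratio of 1.75 in all five scores, all acting in the same direction. Giving the 1.75 effects alternating signs brings it to 11%.

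**Conclusion.** The concern holds for the Group coefficient in the weekly substance-use models. As written, that coefficient is a residual effect given brain change. It is not a clean direct effect either, because common causes of brain change and use are not adjusted for.

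The size is uncertain. Under no true Group effect and a trait-only link, false rejection is about 8% to 29% with the anticipated cue-region shifts and 11% to 13% with one active score. Larger figures need shifts that the plan does not anticipate. Under full mediation, the joint test has essentially no power for the drug effect. All of this assumes the score correlation, the between-participant SD and the transfer of treatment-success odds ratios to weekly use.

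Two wider inferences are not supported. The treatment-success model is not affected, since it fits Group first. The Group-by-Session tests of neural response are not affected, since the change is their outcome and not a covariate.

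**What to change.** In the polysubstance paragraph of section 9.1, state two steps for each substance.

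- First, fit a GEE logistic model with Group, week and the sex stratum, without change scores. Use all treated randomised participants with weekly use data, whether or not they have an ON scan. Take the drug effect from this model. The sample must be named: restricting this step to participants scanned at day 55 would again condition on a post-randomisation event.
- Second, add the neural change scores in participants with both scans, and use this model only to test the scores given Group. State that its Group coefficient is not the treatment effect.

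The cost is a few sentences and one more model fit per substance. No new data are needed.

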4 STUDY PLAN

4.1 Study Design:

Single-blind, prospective study with Phase 1 (N = 60) to show feasibility and Phase 2 (N = 200) to confirm Phase 1 findings if they meet the milestones of effect size. This is to comply with the structure of the two-phase R61/R33 NIH funding mechanism. Both Phases will use the same sequence of data collection ([Section 3.1, Figure 2](#)).

Rationale for the study duration: Early medication effects are considered to be strong predictors of long term effectiveness both at the clinical (e.g. tolerability and symptom relief) and at the neural systems and pharmacodynamic levels (McDermott et al 2015). XRNTX exhibits high drop-out rate in the first 2 months of treatment, with 50% to 75% retention at the 3rd XRNTX injection (Wang et al 2015, Lee et al 2017). In a trial of sublingual buprenorphine, retention at 3 months was approximately 75% and relapse rates defined as repeated opioid positive urines were almost unchanged between 3 and 6 months time points (Lee et al 2017). Thus, a 70-day follow up period provided by two monthly XRNTX or XRBUP injections is a necessary and sufficient time window for a neurobiological evaluation of the mechanisms of relapse vulnerability while minimizing the effect of unrelated variables such as change in family, employment or medical status, on the outcome variable. We optimize the two-phase design by designing experiments that would generate data that could serve two purposes: the initial Phase 1 exploratory and milestone target and then part of the Phase 2 sample that would address confirmatory questions that require a sample size that neither phase could reach separately.

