The clinical management of XRBUP is similar to XRNTX except that induction to XRBUP requires partial detoxification followed a weekly dose of injectable XRBUP, while induction on XRNTX requires complete abstinence (Lofwall et al 2018). The goal of the detoxification and induction phase of the experiment is to establish a uniform starting point for both monthly formulations. To achieve it, we will detoxify all participants to abstinence and randomize after abstinence from illicit opioids has been achieved. Outpatient detoxification to abstinence takes between 5 and 10 days. Following detoxification, the XRBUP participants will receive a combination of 8mg, 16mg, and 24mg strengths of weekly XRBUP, not to exceed 32 mg/week, followed by the injection of 64mg, 96mg, or 128mg of monthly XRBUP. If clinically indicated, supplemental doses of sublingual buropenorphine/naloxone (Suboxone) may be used. If clinically indicated, the induction procedure may be extended by up to one week, using the same approach. The total duration of induction to Brixadi will not exceed 14 days. The XRNTX participants will receive 50 mg of oral naltrexone for 7-10 days after detoxification followed by the 1st XRNTX (380 mg naltrexone IM) injection. The use of symptom-driven titration of weekly XRBUP during induction reflects current best practices in administration of the drug and increases participant safety and comfort. The XRBUP induction period is also intended to synchronize the timepoint at which both cohorts begin their monthly treatments. The non-opioid detoxification will follow the procedure described in our previous neuroimaging studies (Langleben et al 2014, Langleben 2015, Wang et al 2018). Participants who are opioid-positive upon screening will undergo office-based withdrawal management (detox) by the study physicians using FDA-approved generic medications to alleviate opioid withdrawal symptoms following a symptom-triggered approach that includes clonidine 0.1 mg tid, dicyclomine 20 mg qid, clonazepam 0.5 mg q12 hrs PRN, diphenhydramine 25 mg PRN, non-steroidal anti-inflammatory medicines PRN, Trazodone 50 mg qhs and oral hydration solutions (Molenberghs et al 2005). The induction to XRNTX or XRBUP will commence immediately after the baseline MRI session. The 1st monthly injection will be administered by an experienced nurse practitioner after induction is completed (approximately 7-14 days later).

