9 STATISTICAL CONSIDERATIONS

9.1 Statistical Hypotheses

Overview of primary hypotheses: Our primary response will be a binary indicator of treatment failure on the XRNTX or XRBUP regimen, defined as ≥ 2 weekly UDS positive for opioids, or self-report of ≥ 2 periods of three or more days of opioid use, or refusing XRNTX or XRBUP, or dropping out of study entirely. In hypotheses H1a and H1b, we are examining the effects of small, pre-specified, sets of measures, so our analyses will focus on model fit and prediction, and not on model selection. In hypothesis H1c, we search for best sets of predictors among demographic and clinical-behavioral variables, and over sets of brain/neural measures, so our focus is on model selection and on avoiding overfitting to the available data.

R61 Phase:

Hypothesis H1 (fMRI): For each of the cue reactivity (H1a), response inhibition (H1b), and connectivity (H1c) brain measured, we have a small number of neural responses associated with one or two regions of interest. These variables are continuously distributed, so we will test Hypotheses 1a, 1b and 1c using a repeated measures analysis of variance (rm-anova). The models will include a within-subject factor for Session (PRE vs ON) and a between-subject factor Group (XRNTX vs XRBUP), and their interaction. To accommodate the anticipated non-normal distributions of the response, we will use a generalized estimating equation (GEE) approach, using robust standard errors, using a compound symmetry working correlation structure for the within-subject correlations between the PRE and ON fMRI scans (Diggle PJ et al 2002). We will perform the rm-anova separately for each ROI (mPFC and VS for H1a, IFC for H1b, and VS-rtIFG and VS-mPFC for H1c). The hypotheses will be addressed by the Session by Group interaction, and we will obtain estimates and standard errors of the PRE vs ON change within each of the two groups, along with the size, standard error and significance of the differences between these estimates.

Sample size considerations for sample: The sample size is adequate for application of the GEE methods to obtain robust standard error (Lipsitz et al 1994). For a test of the PRE vs ON effect, our sample yields 80% power for a one-sided test that the ON levels will be Cohen's $d=0.4$ lower than the PRE levels, consistent with a decrease of Cohen's $d=0.5$ observed in our preliminary data and a decrease of Cohen's $d=0.3$ in the Suboxone sample.

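### The secondary weekly substance-use GEE has no week term, so unequal time on study plus a common trend in use would leak, slightly, into the Group coefficient

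*Combined protocol and SAP*

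**What the plan says.** Section 9.1, under the polysubstance outcomes, uses self-report and urine screens to "create binary weekly measures of use for each substance". It then plans to "use GEE repeated measures logistic regression models, with Group and the neural change measures as predictors, to estimate and test effects". It calls these analyses secondary, states "We anticipate 25% dropout rates" without splitting the figure by arm, and adds pattern-mixture and selection models as sensitivity analyses for nonignorable missingness. Nothing elsewhere in the document adds week, visit or time to this model, and its working correlation is not stated.

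The imaging GEE in the same section does name its time factor: "The models will include a within-subject factor for Session (PRE vs ON) and a between-subject factor Group (XRNTX vs XRBUP), and their interaction".

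Three other places bear on the point:

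- Section 4.1, on retention: "XRNTX exhibits high drop-out rate in the first 2 months of treatment, with 50% to 75% retention at the 3rd XRNTX injection". For comparison it cites about 75% retention at 3 months in a trial of sublingual buprenorphine.
- Section 6.1, on the starting state: "we will detoxify all participants to abstinence and randomize after abstinence from illicit opioids has been achieved".
- Section 13.1 puts the second scan at Day 55, between the second injection (Day 40) and the third (Day 70).

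**The concern.** As listed, the mean model is logit P(use in week t) = b0 + b1 × Group + b2 × (neural change). Without week, b1 compares each arm's average over whichever weeks that arm supplied. Suppose one arm leaves earlier and use is drifting in the same way in both arms. The arms then average over different stretches of the same curve, and b1 differs from zero although use is identical in every week.

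This does not need informative dropout. Missingness that depends only on arm and week is harmless to a GEE when both are in the mean model, and here only arm is. What is at stake is the Group estimate for weekly opioid, stimulant and benzodiazepine use: some of a reported difference could be a difference in time on study.

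**Working it through.** The plan gives no power, effect size or weekly use rate for this analysis, so there is no stated figure to reproduce. The check asks how far the Group odds ratio moves from a true value of 1.00.

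**Inputs from the documents.** XRNTX retention of 50% at the third injection (low end of the range in section 4.1). Retention of 75% for XRBUP (the sublingual figure in section 4.1, used as a stand-in). Weekly visits from Day 10 to Day 100: (100 − 10)/7 = 12.9, so 13 weeks. Second scan at Day 55: (55 − 10)/7 = 6.4 weeks after the first injection, taken as week 7. 70 per arm (section 9.1).

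**Assumptions.** The same time trend in both arms, with several tried. Dropout at a constant weekly hazard, unrelated to use. The third injection at about week 9.

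**Closed form.** Retention to week t is S(t) = r^((t−1)/8). This gives a mean of 8.1 weeks supplied at r = 0.50 and 10.6 at r = 0.75. Among participants who reach week 7 the means are 11.5 and 12.3, so the scan requirement removes most of the imbalance. Without a week term, the fitted rate in an arm is

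e = Σ P(L) × C(L) / [1 + (L−1)ρ] ÷ Σ P(L) × L / [1 + (L−1)ρ],

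where L is the last week supplied, C(L) is the sum of the weekly use probabilities to week L, and ρ is the working correlation. Example, with use rising from 20% to 50% (linear in the logit), ρ = 0.3, all participants: 0.292 versus 0.317, so OR = (0.292/0.708)/(0.317/0.683) = 0.89, a log odds ratio of −0.12. Limited to those reaching week 7: 0.321 versus 0.331, OR = 0.955, log −0.05.

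Group OR at 50% versus 75% retention, given as ρ = 0 / ρ = 0.3:

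| Trend in both arms | All participants | Reached week 7 |
|---|---|---|
| 20% to 50% | 0.92 / 0.89 | 0.96 / 0.955 |
| 50% to 20% | 1.08 / 1.12 | 1.035 / 1.04 |
| 40% to 10% | 1.10 / 1.15 | 1.04 / 1.05 |
| 40% to 30% | 1.03 / 1.04 | 1.01 / 1.01 |
| flat 30% | 1.00 | 1.00 |

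At 60% versus 75% retention the shifts are roughly halved. At equal retention the OR is exactly 1.00.

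**Simulation.** 70 per arm, 13 weekly binary outcomes, random-intercept SD 2, exchangeable GEE with robust standard errors, two-sided 5% test of Group, 1,000 replicates (Monte Carlo SE about 0.7 to 1.0 points). The change scores were not simulated; restriction to participants reaching week 7 stands in for having one.

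| 50% vs 75% retention | No week term | Linear week term |
|---|---|---|
| All, use 5% to 40% | 10.8% | 5.1% |
| All, use 5% to 20% | 8.5% | 6.2% |
| All, use 40% to 10% | 8.4% | 5.4% |
| Reached week 7, 5% to 40% | 6.9% | 5.4% |

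Controls without week: 5.6% at 75% versus 75% retention with use rising 5% to 40%, and 5.1% with a flat 20% trend.

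Repeat runs of the 5% to 40% case in all participants gave a bias of −0.19 to −0.20 on the log odds ratio and 10.0% to 11.2% rejection; with week, −0.01 and 5.7%. Repeat runs limited to participants reaching week 7 gave −0.06 to −0.08 for that rising trend and +0.04 to +0.05 for falling use. Rejection across the week-7 repeats at this retention was 5.2% to 6.8%. A separate set with random-intercept SD 1.5 and 300 runs per scenario gave 6.7% to 8.7% in all participants without week, accurate to about ±2.5 points.

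**The case against.** A reader might infer that the weekly-use analysis has about twice its nominal error rate and is tilted towards XRNTX. The documents do not support that, for four reasons.

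- **The listed model contains change scores.** Anyone without the Day 55 scan has none, and no imputation is planned. The 8% to 11% figures belong to a Group model fitted in everyone, which is not the one written. This objection stands.
- **The direction is not fixed.** Detoxification to abstinence makes a rising trend arguable for opioids. Section 6.1 sets no such starting point for stimulants or benzodiazepines, and a falling trend reverses the sign. This also stands.
- **Unequal follow-up is possible, not stated.** The 50% to 75% range for XRNTX reaches the 75% comparator, and that comparator is a different formulation. Sections 3.4 and 4.4 invite people who stop medication to continue follow-up visits, so weekly data may outlast injections. At 62.5% versus 75% retention, with all participants, rejection was only 6.1%.
- **The planned sensitivity analyses would catch much of it.** A pattern-mixture fit compares arms within dropout pattern. In a run with all participants, weighting by the true inverse retention probability cut the bias from −0.19 to −0.01 and rejection to 5.3%. These remain sensitivity analyses for missing data, however, and they leave the main model without week.

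The phrase repeated measures could be taken to imply a time factor, but it describes the correlation among observations. The imaging model shows that the authors name time when they intend it.

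**Conclusion.** The omission is real and the mechanism is confirmed. Bias needs both unequal time on study and a common trend, and it disappears if either is absent or once week is modelled. In the model as written, limited to participants with a Day 55 change score, it is small: about 0.04 to 0.08 on the log odds ratio for the steeper trends, less for shallow ones, with a false-positive rate of about 5% to 7%. Fitting Group in all participants would raise this to about 0.1 to 0.2 and 8% to 11%. All these figures rest on assumed weekly trends, on 50% versus 75% retention, and on dropout unrelated to use.

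It would be wrong to read this as a threat to the main conclusions. The H1 model contains Session, and the treatment-failure outcome is a single binary result per participant, so neither is affected. Opioid use is also measured by the last-month urine endpoint in section 3.2. This is a minor improvement to a secondary analysis.

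**What to change.** In the polysubstance paragraph of section 9.1:

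1. Add week, either categorical or linear plus quadratic, to every weekly-use GEE, and state the working correlation.
2. Fit Group with week first in all participants, then add the neural change scores. This follows the order section 9.1 already uses for the treatment-success logistic model, and it keeps the Group comparison from being conditional on reaching a post-randomization scan. The two changes belong together, since Group in all participants without week would carry the larger bias.
3. Optionally add Group-by-week and report Group as a contrast averaged over the same weeks in both arms.

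The cost is a few lines of SAP text and a few parameters, with no new data or participants. The optional interaction costs a little precision.
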